16.1.9 Documentation on Statistical Methodology

Confidential

the subscale should be tabulated without missing. If “No” is chosen in question 16, the question 16 should be treated as missing.

Table 4.13.2 Step 2 in KDQOL scoring [2]

- Each item score should be averaged to calculate each subscale score

Subscale	Number of items	After scoring according to Table 4-1, the mean of the items included in each subscale should be calculated.
Kidney disease-specific scale		
Symptoms	12	Questions 14 A–K, L (M)*
Effects of kidney disease on daily life	8	Question 15 A–H
Burden due to kidney disease	4	Question 12 A–D
Working status	2	Question 20, Question 21
Cognitive function	3	Question 13 B, D, F
Relationship with people	3	Question 13 A, C, F
Sexual function	2	Question 16 A, B
Sleep	4	Question 17, Question 18 A–C
Social support	2	Question 19 A, B
Encouragement from dialysis staff	2	Question 24 A, B
Patient satisfaction with dialysis care	1	Question 23
Comprehensive scale (SF-36)		
Physical functioning	10	Question 3 A–J
Daily role functioning (physical)	4	Question 4 A–D
Bodily pain	2	Question 7, Question 8
General health	5	Question 1, Question 11 A–D
Vitality	4	Question 9 A, E, G, I
Social functioning	2	Question 6, Question 10
Daily role functioning (emotional)	3	Question 5 A–C
Mental health	5	Question 9 B, C, D, F, H

4.14 Adverse drug reactions

Adverse events for which a causal relationship to the study drug was evaluated as “reasonable possibility” are defined as adverse drug reactions.

5. Analysis Sets

Efficacy analysis will be performed in the largest analysis set (hereinafter, FAS). Safety analysis will be performed in the safety analysis set.

The analysis sets are defined below; for details on the treatment of subjects in the final fixation data, the FAS is the analysis set consisting of subjects randomized by the sponsor until data fixation, excluding the following subjects.

5.1 Efficacy analysis set

(1) FAS

The FAS consists of all randomly allocated subjects excluding the following subjects:

- ✓ Subjects who did not have anemia associated with NDD-CKD
- ✓ Subjects who have never received a dose of the study drug
- ✓ Subjects with no post-randomization efficacy data

5.2 Safety analysis set

The analysis set consisting of all randomly allocated subjects excluding the following subjects is the safety analysis set.

- ✓ Subjects who have never received a dose of the study drug
- ✓ Subjects with no post-randomization safety data

6. Patient Cohorts

The patient cohorts are defined below. Each patient cohort will be analyzed as needed.

- ✓ Correction cohort: A group of patients who have not received ESA formulations from 8 weeks prior to the first day of the screening period.
- ✓ Conversion cohort: A group of patients who have received ESA formulations from 8 weeks prior to the first day of the screening period.
- ✓ Conversion (Hb values ≥ 11.0) cohort: A subset of patients in the Conversion cohort whose mean Hb value during the last 2 screening sessions is ≥ 11.0 g/dL.

- ✓ Conversion (Hb values < 11.0) cohort: A subset of patients in the Conversion cohort whose mean Hb value during the last 2 screening sessions is <11.0 g/dL.

7. Data Handling

Final fixed data should be handled as follows:

7.1 Handling of missing data

If test measurements are missing or if problems with samples etc. result in invalid measurements or reference values, these should be handled as missing values. Derived variables should also be treated as missing if even one test value or other data required for derivation is missing or not adopted.

7.2 Handling of data for tabulation at each evaluation time point

Data that meet the permitted range specified in the “Table 9.1-1 Permitted range of study visits” section of the protocol should be used for the tabulation at each evaluation time point and should not be imputed with those outside the permitted range.

If there are multiple data within the permitted range, then the one closer to the reference date should be adopted. If the deviations from the reference date are the same, data for the efficacy and safety evaluations should be adopted before and after the reference date, respectively.

7.3 Handling of efficacy endpoints if rescue therapy is performed

If rescue therapy is performed, data from the day after rescue therapy should not be used to assess efficacy.

7.4 Imputation of missing values

The mixed repeated-measures model (MMRM) should not use data imputing missing data, except for the first day of the treatment period.

If there are missing values at the first day of the treatment period, data from the day closest to the first day of the treatment period should be used as data for the first day of the treatment period.

In the case of missing data in calculating descriptive statistics of mean Hb values at Weeks 48 and 52 of the treatment period, missing data should be imputed with data from the evaluation time point immediately before the missing evaluation time point (excluding the first day of the treatment period) (LOCF method). When any one evaluation time points has missing values, the data at the evaluation time point closest to the missing evaluation time point is adopted, and when two evaluation time points

have missing values, the data in the two different evaluation time points closest to and before the missing evaluation time points should be adopted to calculate the mean Hb value. However, Hb values at the same evaluation time point should not be used.

In addition, for clinical laboratory values, vital signs, and QOL indices among the efficacy endpoints, values at Week 52 of the treatment period imputed with data from the immediately preceding evaluation time point (excluding the first day of the treatment period) should also be output.

7.5 Handling of clinical laboratory test values, such as those less than the limit of quantification

If the measured values are reported to be not more than the limit of quantification, less than the limit of quantification, or impossible to calculate, the following handling procedures should be applied for tabulation, and missing values or zero values should not be used.

[Handling of quantification limit values]

(1) If the measurement is reported as less than the limit of quantification

The value obtained by adding the following processing to the limit of quantification value is used as an alternative value for tabulation.

- 1) After checking the number of significant figures of the applicable item, 1 should be subtracted from the significant figure of the lowest reported quantification limit value.
- 2) It should then be expanded by one digit to a smaller number and 9 is set.

Example) Report: less than 3 Effective number of the measuring facility: up to ones digit

→ Tabulation handling: 2.9

Report: less than 500 Effective number of the measuring facility: up to tens digit

→ Tabulation handling: 499

- (2) When the measured value is reported as not more than the limit of quantification or not less than the upper limit of quantification, the limit of quantitation itself should be used as a substitute value for tabulation.

Example) Not more than the limit of quantification

Report: ≤ 10 → Tabulation handling: 10

Not less than the limit of quantification

Report: ≥ 20 → Tabulation handling: 20

(3) When the measured value used in the calculation is less than or not more than the quantification limit and the test result is reported as “Unable to be calculated” (Urinary albumin/creatinine ratio, urinary protein/creatinine ratio), the measured value used in the calculation is added with the above processing as an alternative value, calculation is performed using the following calculation formula, and the calculation result is used for tabulation.

[Arithmetic expression]

- Urine albumin/creatinine ratio = $100 \times \text{Urine albumin}/\text{urine creatinine}$
- Urine protein/creatinine ratio = $1000 \times \text{Urine protein assay (concentration)}/\text{urine creatinine}$

8. Statistical Method

In this trial, when the observation of all subjects is completed, the final data will be fixed and the statistical analysis should be conducted.

8.1 Basic matters

8.1.1 Level of significance and confidence coefficient

When implementing tests, level of significance should be set at 2-sided 5%. CI will be 2-sided with a confidence coefficient of 95%.

8.1.2 Descriptive statistics to calculate

Types of continuous variables to be calculated for each descriptive statistics item are provided below. Number of subjects, mean, standard deviation (SD), median, minimum, maximum, and 2-sided 95% CI of the mean

8.1.3 Number of digits displayed

The number of digits to be displayed in the analysis results will be as follows.

Numeric content	Number of display digits
p value	3 decimal places, however, when it is less than 0.001, it will be described as “< 0.001”.
Proportion (percentage)	Integer part + 1 decimal place
Rate of change	Integer part + 1 decimal place
Descriptive statistics (minimum and maximum)	Same as the number of digits as original variable
Descriptive statistics (mean, SD, median)	Number of digits of the original variable + 1 digit
Rate of increase in Hb value	Integer part + 4 decimal places
QOL (EQ-5D-5L) index value	Integer part + 3 decimal places

Hepcidin will be measured in units of pg/mL; however, the unit used for tabulation should be ng/mL, and the number of displayed digits should be two decimal places.

8.2 Breakdown of subjects

8.2.1 Disposition

For subjects enrolled in the treatment period, the breakdown of each analysis set in each treatment group should be provided. The breakdown of patient cohort will also be provided.

Items: Number of subjects enrolled in treatment period, number of subjects completed treatment period phase 2, number of subjects discontinued the study, number of subjects who received rescue therapy, number and proportion of subjects in the FAS, number and proportion of subjects not included in the FAS, number and proportion of subjects in the safety analysis set, number and proportion of subjects not included in the safety analysis set

8.2.2 Subjects who discontinued or interrupted their treatment

For subjects enrolled in the treatment period, the number and proportion of discontinued subjects should be calculated in each treatment group and by reasons for discontinuation. Subjects who entered specific comments ("Criterion for liver function") according to the input rules should be counted for the number of subjects discontinued by reasons that meet the discontinuation criteria for abnormal hepatic function values.

Items: Number and proportion of discontinued subjects by treatment group and the number and proportion of reasons for discontinuation for subjects enrolled in treatment period,

In addition, for subjects enrolled in the treatment period, the number and proportion of discontinued subjects should be calculated in each treatment group and in every 12 weeks (unit: from first day of the treatment period [Day 1] to Day 84, Days 85–168, Days 169–252, and after Day 253.

Items: Number and proportion of subjects discontinued in each treatment group in subjects enrolled in the treatment period

For subjects enrolled in treatment period, the number cases of drug interruption should be tabulated by treatment group and the number and proportion of cases by reasons for interruption should be tabulated. The denominator of the proportion should be the sum of the number of interruption cases. If there are multiple reasons for a single interruption, they should be counted for each reason and stated as the number of interruption cases. For drug interruption due to abnormal hepatic function, subjects who entered specific comments according to the input rules ("Criterion for liver function") should be calculated.

Items: Number of drug interruptions in subjects enrolled in the treatment period and number and ratio of drug interruptions by reasons for drug interruption

8.3 Demographic and other baseline characteristics

For each analysis set, the key demographic and other baseline characteristics for each treatment group should be summarized. Frequency and proportion will be provided for discrete variables and descriptive statistics for continuous variables (no calculation of 95% CI of the mean). The data should also be summarized in the FAS by patient cohort.

Table 8.3.1 Demographic and other baseline characteristics

Category	Item	Type of variables
Subject background	Sex (male, female)	Dichotomous
	Age (years) as of informed consent	Continuous
	2 categories: <65, ≥65	Dichotomous
	2 categories: <75, ≥75	Dichotomous
	Duration of nephrogenic anemia (years)	Continuous
	3 categories: <1, 1 to <5, ≥5	Ordinal
	Height (cm)	Continuous
	Body weight (kg)	Continuous
	BMI (kg/m ²)	Continuous
	2 categories: <25, ≥25	Dichotomous
Race	Race	Multiple value
	3 categories: not Hispanic or Latino, Hispanic or Latino, Unknown	
Ethnicity	Ethnicity	Polytomous
	3 categories: Asian (Japanese), Asian (other), other	
Smoking status	Presence or absence of smoking status 3 categories: never smoked, ex-smoker, current smoker	Polytomous
Underlying cause of CKD	Underlying cause 8 categories: diabetes mellitus, hypertension, autoimmune/glomerulonephritis/vasculitis, interstitial nephritis/pyelonephritis, cystic/hereditary/congenital disease, neoplasm/tumor, unknown, other	Polytomous
Complication	Presence or absence of complications on the first day of the treatment period	Dichotomous
	Presence or absence of hypertension	Dichotomous
	Presence or absence of diabetes mellitus	Dichotomous
	Presence or absence of dyslipidemia	Dichotomous

Previous ESA formulation (Conversion cohort only)	Types of previous ESA formulation 4 categories: epoetin alfa or epoetin beta, darbepoetin alfa, epoetin beta pegol, other.	Polytomous
	Frequency of administration by type of previous ESA formulation 7 categories: once a week, twice a week, three times per week, every 2 weeks, every 3 weeks, every 4 weeks, other	Polytomous
	Weekly dose (IU) of epoetin alfa or epoetin beta	Continuous
	Weekly dose of darbepoetin alfa (µg)	Continuous
	Weekly dose of epoetin beta pegol (µg)	Continuous
Evaluation data	Hb value (g/dL) on the first day of the treatment period	Continuous
	3 categories: <9, 9 to <11, ≥11	Ordinal
	eGFR on the first day of the treatment period (mL/min/1.73 m ²)	Continuous
	4 categories: <15, 15 to <30, 30 to <60, ≥60	Ordinal
	Liver function test (U/L) on the first day of the treatment period	
	3 categories: AST and ALT are both not more than the upper limit of normal, either is more than the upper limit of normal and both are not more than 2 times the upper limit of normal, either is more than 2 times the upper limit of normal	Trichotomous
	CRP (mg/dL) on the first day of the treatment period	Continuous
	Serum ferritin (ng/mL) on the first day of the treatment period	Continuous
	2 categories: <100, ≥100	Dichotomous
	TSAT (%) on the first day of the treatment period	Continuous
	2 categories: <20, ≥20	Dichotomous

	With or without iron supplements on the first day of the treatment period	Dichotomous
	2 categories: oral, intravenous	Dichotomous
	With or without iron-containing phosphate binders on the first day of the treatment period	Dichotomous

8.4 Study drug administration/treatment period and study drug administration/compliance status

For FAS and safety analysis set, the descriptive statistics of the study drug administration/compliance rate (no calculation of 95% CI of the mean) will be calculated by treatment group to provide the number and rate of subjects with study drug compliance rate of $\geq 80\%$ and $< 80\%$. Analysis should be performed by patient cohort in the FAS.

For FAS and safety analysis set, the descriptive statistics of the study drug administration/treatment period (no calculation of 95% CI of the mean) will be calculated by treatment group. Analysis should be performed by patient cohort in the FAS.

For FAS and safety analysis set, the descriptive statistics of the cumulative dosage of study drug (no calculation of 95% CI of the mean) will be calculated by treatment group.

8.5 Efficacy analysis

As a general rule, efficacy analysis will be performed on the FAS. When necessary, descriptive statistics for continuous variables should be calculated and frequency and proportion will be calculated for discrete variables. Unless otherwise specified, a similar analysis will be conducted for patient cohort. No data from the day after the rescue therapy implementation date should be included in the efficacy analysis.

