8.5.3 Rescue therapy

The following rescue therapy options will be available for subject safety. If any of the following rescue therapies are performed prior to scheduled tests at Week 24 of the treatment period, that subject will be withdrawn from the study. If rescue therapies are performed after scheduled tests at Week 24 of the treatment period, the subject can continue in the study unless investigators/subinvestigators determine study withdrawal is appropriate. Details of any rescue therapy implemented will be recorded in the subject's CRF.

(1) ESA formulations

If a subject has received maximum dosages of MT-6548 or darbepoetin alfa injection for ≥ 2 weeks and meets all criteria below, investigators/subinvestigators may administer ESA as rescue therapy to improve Hb levels if necessary in order to secure subject safety. ESA rescue therapy may also be administered without meeting the criteria below if deemed necessary by investigators/subinvestigators in order to secure subject safety, such as in cases of acute decreases in Hb. Study drug administration (MT-6548 or darbepoetin alfa injection) will be discontinued if implementing ESA rescue therapy. Study drug treatment may resume if Hb levels improve, as long as there is no concomitant use with ESA. Subjects who are not expected to resume study drug treatment will be withdrawn from the study.

Administration of any ESA formulation aside from darbepoetin alfa injection is considered rescue therapy for subjects in the darbepoetin group. Dosage increase of darbepoetin alfa injection (regardless of adherence to the dosage adjustment algorithm) does not constitute rescue therapy.

- ✓ Anaemia or anaemia symptoms (e.g., fatigue, weakness, shortness of breath, chest pain, confusion, dizziness) become aggravated compared to the first day of the treatment period to the point they are clinically problematic.
- ✓ Hb levels drop to < 8.0 g/dL.

(2) RBC transfusion

Normally RBC transfusions are performed when clinically necessary in instances of acute or major haemorrhaging. RBC transfusion may be performed at investigator/subinvestigator discretion if deemed clinically necessary in cases of potentially worsening anaemia, even if that

anaemia is not severe, or in cases of moderate to severe anaemia symptoms.

(3) Phlebotomy

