13.2 Data handling

(1) Definition of missing values

If test measurements are missing or if problems with samples etc. result in invalid measurements or reference values, these are handled as missing values.

(2) Handing of timepoint data for statistical summaries at each measurement timepoint

Statistical summaries for each evaluation timepoint will use data compliant with permitted ranges as described in “Table 9.1-1 Permitted ranges for study center visits.” There will be no supplementing with data from outside the permitted range.

If multiple data points exist within the permitted range, then the one closest to the scheduled day will be used. If there are deviations from the scheduled day, then data points prior to the scheduled day will be used for efficacy evaluation, and data points after the scheduled day will be used for safety evaluation.

(3) Handling of efficacy endpoints if rescue therapy was implemented

No data obtained after implementation of rescue therapy will be used for efficacy evaluation.

(4) Imputation of missing values

Mean Hb values for treatment period Weeks 20 and 24 imputed using LOCF, a method by which missing timepoints are imputed using data from the immediately prior timepoint (excluding

the treatment period start date), will be derived as data for analysis of covariance (ANCOVA) performed as sensitivity analysis for the primary efficacy endpoint. If 1 value is missing, then the closest value to the missing one will be used; if 2 values are missing, then mean Hb will be calculated using 2 different prior values closest to the missing value. Two values from the same timepoint will not be used.

Values imputed by LOCF will also be derived for treatment period Weeks 24 and 52. Data from treatment period Week 24 with missing values imputed will be used as data from the completion of treatment period Phase 1, and data from treatment period Week 52 with missing values imputed will be used as data from the completion of treatment period Phase 2.

(5) Handling of PK-related data

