3.1.2 Other endpoints

- (1) Changes in mean Hb values from the first day of the treatment period at Weeks 48 and 52 of the treatment period
- (2) Proportion of subjects with a ≥ 1.0 g/dL increase in mean Hb values from the first day of the treatment period at each time point of the treatment period.
- (3) Number of days to maintain the target Hb values
- (4) Proportion of subjects receiving rescue therapy with ESA formulations, red blood cell transfusion, or phlebotomy
- (5) Study drug dosage

- (6) Total number of dosage adjustments
- (7) Iron supplement dosage
- (8) Proportion of subjects receiving oral, intravenous, or (any route) administration of iron supplements
- (9) Proportion of subjects with serum ferritin ≥ 100 ng/mL or TSAT $\geq 20\%$.
- (10) Changes and rate of changes in iron-related indices (serum iron, TIBC, TSAT, and serum ferritin values) and hepcidin from the first day of the treatment period
- (11) Changes in hematocrit, red blood cell count, reticulocytes (number and rate), mean corpuscular volume, mean corpuscular hemoglobin, and erythropoietin (MT-6548 group only) from the first day of the treatment period
- (12) Changes and rate of changes in systolic blood pressure, diastolic blood pressure, lipids (total cholesterol, LDL-C, HDL-C, LDL-C/HDL-C ratio, triglycerides), and blood glucose from the start of the treatment period
- (13) Change in renal function-related indices (eGFR, serum creatinine, urinary albumin/creatinine ratio) from the first day of the treatment period
- (14) QOL indices (EQ-5D-5L, KDQOL)

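### Filing renal, blood-pressure, lipid and glucose measures as efficacy endpoints makes the rescue rule drop their observed post-rescue values from the only between-group and threshold analyses

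*SAP*

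**What the plan says.** The final SAP states the rescue rule twice, with no exception by endpoint. Section 7.3: "If rescue therapy is performed, data from the day after rescue therapy should not be used to assess efficacy". Section 8.5: "No data from the day after the rescue therapy implementation date should be included in the efficacy analysis". Protocol 13.2 (3) has the parent rule: "No data obtained after implementation of rescue therapy will be used for efficacy evaluation".

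Under 3.1 Efficacy endpoints, section 3.1.2 of the final SAP lists, as item (12), "Changes and rate of changes in systolic blood pressure, diastolic blood pressure, lipids (total cholesterol, LDL-C, HDL-C, LDL-C/HDL-C ratio, triglycerides), and blood glucose" and, as item (13), "Change in renal function-related indices (eGFR, serum creatinine, urinary albumin/creatinine ratio) from the first day of the treatment period". Both are analysed in 8.5.2, inside the section that the rule governs. Section 7.4 confirms the filing when it calls for a carried-forward Week 52 output "for clinical laboratory values, vital signs, and QOL indices among the efficacy endpoints".

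The protocol files them differently. Its efficacy list (5.4.1) contains none of these measures. Laboratory values and vital signs appear under safety (5.4.2, with details in 9.2.4.1). Section 10 of the final SAP nevertheless declares no change from the protocol.

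On rescue itself, Protocol 8.5.3 withdraws any subject rescued before the Week 24 tests. After that point, "the subject can continue in the study unless investigators/subinvestigators determine study withdrawal is appropriate".

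**The concern.** The protocol applied its rescue exclusion to a list made up of Hb, red-cell, iron, dosing and QOL endpoints. For those the logic is easy to see, because an ESA, a transfusion or a phlebotomy acts directly on Hb. The protocol gives a similar reason for withdrawing rescued subjects before Week 24 (12.1): MT-6548 efficacy could not be judged accurately. Once the SAP adds renal function, blood pressure, lipids and glucose to the efficacy list, the same rule governs them, and neither document gives a reason for that.

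The study has long-term safety as a stated objective, and the formal Week 52 comparisons of renal function and blood pressure sit only in 8.5.2. If rescue is related to renal or cardiovascular course, or its frequency differs between arms, those comparisons rest on a selected set of observations although the missing values were measured.

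**Working it through.** No figure in the plan needs reproducing. The check is a trace through the sections, followed by an illustration of size.

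**Step 1: which analyses lose data.**

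| Measure | Analysis in 8.5.2 (FAS, rescue rule applies) | Analysis in 8.6 (safety set, no rescue exclusion) |
|---|---|---|
| Blood pressure | (12): between-group MMRM, paired t-test | 8.6.6: descriptive values and changes |
| Lipids, glucose | (12): between-group MMRM, paired t-test | 8.6.2: descriptive values and changes |
| eGFR, creatinine | (13): MMRM; eGFR fall ≥30% and ≥40%; creatinine ≥2-fold; Fisher tests | 8.6.2: descriptive values and changes |
| Urine albumin/creatinine ratio | (13): MMRM; shift table | 8.6.2: descriptive values and changes |

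The safety tables omit even the 95% CI of the mean. The between-group estimates, the threshold proportions and the albuminuria shift table have no counterpart free of the exclusion.

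**Step 2: which subjects.** Rescue before the Week 24 tests leads to withdrawal, so almost nothing is collected afterwards for the rule to remove. The Phase 1 SAP has the same structure (3.1.3, 7.3, 8.5, 8.5.3), but for this reason little turns on it there. The rule matters for subjects rescued after Week 24 who remain.

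**Step 3: how much per subject.** Chemistry and blood pressure are scheduled at Weeks 28, 32, 36, 40, 44, 48 and 52, so up to 7 visits. The albumin/creatinine ratio is scheduled at Weeks 36 and 52, so up to 2. Pre-rescue visits stay in the MMRMs. In the carried-forward Week 52 output of 7.4, an excluded Week 52 value could be replaced by an older pre-rescue one, if excluded values are handled as missing.

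**Step 4: size, under assumptions.** The documents give no rescue rate and no eGFR-fall risk; all inputs here are assumed. Let *r* be the share rescued after Week 24 who have a Week 52 value, *p1* their risk of an eGFR fall ≥30%, and *p0* the risk in the others. Take the denominator as subjects with an admissible Week 52 value, since the SAP does not state it.

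- Reported proportion = *p0*
- Proportion with all observed data = *r·p1* + (1 − *r*)·*p0*
- Understatement = *r*·(*p1* − *p0*)
- Share of events excluded = *r·p1* / [*r·p1* + (1 − *r*)·*p0*]

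With *p0* = 15% and *p1* = 40%:

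| *r* | Reported | All observed | Understatement (points) | Events excluded |
|---|---|---|---|---|
| 3% | 15.0% | 0.0120 + 0.1455 = 15.75% | 0.75 | 7.6% |
| 5% | 15.0% | 0.0200 + 0.1425 = 16.25% | 1.25 | 12.3% |
| 10% | 15.0% | 0.0400 + 0.1350 = 17.5% | 2.5 | 22.9% |

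With *p0* = 20% and *p1* = 40–60%, the all-observed proportion is 20.2–20.4% at *r* = 1%, 20.6–21.2% at 3%, 21.0–22.0% at 5% and 22.0–24.0% at 10%, against 20.0% reported. If *p1* = *p0* the understatement is zero and only precision is lost. If *p1* < *p0* the sign reverses.

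**Step 5: between arms.** With common *p0* = 15% and *p1* = 40% and rescue in 8% against 2%, the difference removed is (0.08 − 0.02) × (0.40 − 0.15) = 1.5 points, about 0.015 × 150 = 2.25 subjects in an arm of 150. The 95% half-width for a difference at 15% per arm is 1.96 × √(2 × 0.15 × 0.85 / 150) = 8.1 points.

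**The case against.** The strongest case for the plan has four parts.

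- **The data are still reported.** A reader might infer that post-rescue eGFR, creatinine and blood pressure are lost. They are not: 8.6.2 and 8.6.6 tabulate them by arm and visit, with changes, in the safety set. This stands, and it narrows the point to the inferential and threshold analyses.
- **Rescued subjects need not be sicker.** A reader might infer that the Week 52 comparisons are biased towards healthier subjects. Protocol 8.5.3 links transfusion to haemorrhage and ESA rescue to low Hb with worsening symptoms. It also counts phlebotomy for high or fast-rising Hb as rescue, and nothing links rescue to inflammation or renal decline. The direction of any bias is therefore not established.
- **Excluding post-rescue data is defensible.** ESA rescue stops study drug (Protocol 8.5.3), and in the MT-6548 group it supplies a drug of the comparator's class. Later values then mix the treatments being compared. This stands as a reason to keep the planned version, so a reader should not infer that the rule is an error to be struck out. It is weaker for transfusion and phlebotomy, where stopping study drug is not required.
- **The stakes are limited.** These are the lowest tier of efficacy endpoints, the Phase 1 SAP (8.5.4.7) treats that tier as exploratory, and the assumed between-arm effect in Step 5 is small against its confidence interval. This also stands.

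None of this answers the central observation: measured renal and blood-pressure values leave the only formal comparisons because of where the SAP files them.

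**Conclusion.** The point holds in limited form. Because of the filing in 3.1.2 (12)–(13), sections 7.3 and 8.5 remove observed post-rescue values from the MMRMs, the eGFR-fall and creatinine-doubling proportions and the albuminuria shift table in 8.5.2. The conclusion rests on the SAP being applied as written, and it concerns Weeks 24 to 52 only.

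Its size cannot be computed from the documents. The figures above (0.2 to 4 points across the assumed ranges for a single-arm proportion, zero if risks are equal) show only how the effect scales with the rescue rate and the difference in risk. Selection bias is a risk of unknown and possibly small size, not a demonstrated result. The primary endpoint, the non-inferiority conclusion and the sample size are untouched.

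**What to change.** Keep the exclusion for Hb, erythropoietic, iron and QOL endpoints; QOL must stay under it because Protocol 5.4.1 lists QOL as efficacy and 13.2 (3) bars post-rescue efficacy data. Add a repeat of 8.5.2 (12)–(13), including the eGFR and creatinine threshold analyses and the albuminuria shift table, using all observed values within the visit windows whether or not rescue was given. Report it as a safety analysis in the safety analysis set, beside the planned version, and state the denominator of each proportion and the number of subjects with post-rescue values in each arm. Record the addition, and the filing of these measures as efficacy endpoints, in section 10 of the final SAP.

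The cost is a short SAP addition, a changed data filter and a few extra tables; no new data are needed, and the sponsor has already used an additional SAP to add a table. The drawback is that post-rescue values in the MT-6548 group may reflect ESA exposure, which is why both versions should be shown.
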